## 9. STATISTICAL CONSIDERATIONS

### 9.1. Statistical Hypotheses

The primary objective of the study is to describe the safety and tolerability of high dose ascending intravenous sotrovimab administered over different infusion times. No formal statistical hypothesis testing is planned.

### 9.2. Sample Size Determination

A sample size of approximately 200, and up to 500 participants (with 300 participants designed to be included through optional cohorts as determined by the Joint Safety Review team (JSRT)) was selected to assess the safety profile of an increased dose of sotrovimab robustly and efficiently. Adverse events with a frequency of  $\geq 1\%$  and  $< 10\%$  are considered common/frequent as per the 2nd edition of the CIOMS Working Groups III and IV ([CIOMS 1999](#)).

The first cohort, Cohort A, will include approximately 200 participants dosed at 2000 mg IV with an infusion time of 60 minutes. With 200 participants, there is a 90% chance of observing at least one particular adverse event of interest, if the true incidence rate of that adverse event is not below 1.14%. Of note, in COMET-ICE, the infusion related reaction (IRR) rate was 1.14%.

Cohort B1 is optional and can occur after Cohort A if there are no significant safety signals or concerns found in Cohort A. It would include approximately 50 participants dosed at 2000 mg with an infusion time of 30 minutes. With 50 participants, there is a 90% chance of observing at least one particular adverse event of interest, if the true incidence rate of that adverse event is not below 4.5%.

Cohort B2 is optional and can occur after Cohort B1 if there are no significant safety signals or concerns found in Cohort A or B1. It would include approximately 50 participants dosed at 2000 mg with an infusion time of 15 minutes. With 50 participants, there is a 90% chance of observing at least one particular adverse event of interest, if the true incidence rate of that adverse event is not below 4.5%.

Cohort C is optional and can occur after Cohort A if there are no significant safety signals or concerns found in Cohort A. It would include approximately 200 participants dosed at up to 3000 mg IV with an infusion time of 90 minutes (if 3000 mg IV is selected). With 200 participants, there is a 90% chance of observing at least one particular adverse event of interest, if the true incidence rate of that adverse event is not below 1.14%.

Cohorts B1, B2 and C will all be considered optional cohorts and will be opened following completion of Cohort A following assessment by the JSRT.

The precision of event rate estimation is shown in the table below, as indicated by the width of 95% confidence intervals. More specifically, the total number of 500 participants reflects the precisions when summarizing over all cohorts, and the total number of 300 participants reflects the precisions when summarizing over all 2000 mg cohorts.

VIR-7831  
Vir Biotechnology, Inc.

VIR-7831-5008 (GSK Study 217114)  
Amendment 4

**Table 2: Precision of Estimated Event Rate**

Total Number of Participants	Number of Participants with a Particular Event	Event Rate	95% Confidence Interval
500 (overall study size, including Cohorts A, B1, B2, and C)	3	0.5%	(0.12%, 1.74%)
	5	1.0%	(0.33%, 2.32%)
	10	2.0%	(0.96%, 3.65%)
	25	5.0%	(3.26%, 7.29%)
	50	10.0%	(7.51%, 12.97%)
	250	50.0%	(45.53%, 54.47%)
300 (combined number of participants dosed at 2000 mg, includes Cohorts A, B1 and B2)	2	0.5%	(0.08%, 2.39%)
	3	1.0%	(0.21%, 2.89%)
	6	2.0%	(0.74%, 4.30%)
	15	5.0%	(2.83%, 8.11%)
	30	10.0%	(6.85%, 13.97%)
	150	50.0%	(44.20%, 55.80%)
200 (individual study size for Cohorts A or C)	1	0.5%	(0.01%, 2.75%)
	2	1.0%	(0.12%, 3.57%)
	4	2.0%	(0.55%, 5.04%)
	10	5.0%	(2.42%, 9.00%)
	20	10.0%	(6.22%, 15.02%)
	100	50.0%	(42.87%, 57.13%)
50 (individual study size for cohorts B1 or B2)	0	0.5%	(0.00%, 7.11%)
	1	1.0%	(0.05%, 10.65%)
	1	2.0%	(0.05%, 10.65%)
	3	5.0%	(1.25%, 16.55%)
	5	10.0%	(3.33%, 21.81%)
	25	50.0%	(35.53%, 64.47%)

### 9.3. Analysis Sets

For the purposes of analysis, the following main analysis sets are defined:

Participant Analysis Set	Description
Safety	All participants who were enrolled and exposed to study intervention. Participants will be summarized according to actual dose and infusion time received during the study.
Intent-to-Treat (ITT)	All participants who were randomized and exposed to study intervention. Participants will be summarized according to the dose they were assigned to.
Pharmacokinetic	All participants in the Safety analysis set who had at least 1 non-missing PK assessment (post-dose non-quantifiable [NQ] values will be considered as non-missing values). Participants will be summarized according to treatment which they received.
Virology	All participants who were enrolled and with a lab confirmed quantifiable nasopharyngeal swab at Day 1. Participants will be summarized according to actual dose received during the study. This will be the primary analysis set for virology.

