d On Day 1, sample collection will occur pre-dose.

e Electrocardiogram at screening only for participants with a history of cardiovascular disease or diabetes

f On Day 1, PK sample will be collected pre-dose and at the end of infusion

g Adverse events will be assessed up to Week 12 post dose. Serious adverse events (SAEs) will be assessed up to Week 36.

VIR-7831  
Vir Biotechnology, Inc.

VIR-7831-5008 (GSK Study 217114)  
Amendment 4

h Participants may be tested at screening if symptom onset  $\leq$  7 days, but dosing (D1 visit) must also occur  $\leq$  7 days of symptom onset.

i Week 8, Week 16, Week 28, Week 32 and Week 36 are planned as site phone calls to participants only.

j If subject withdraws early from the study prior to Week 24, then the W24 visit assessments will be performed as the EW visit. If subject withdraws early from the study after Week 24, the W36 visit assessments will be performed as the EW visit.

k Cohort A 2000 mg to be infused over 60 minutes, Cohort B1 2000 mg to be infused over 30 minutes, Cohort B2 2000 mg to be infused over 15 minutes, Cohort C (up to 3000 mg to be infused over 90 minutes if 3000 mg is selected)

l Note, randomization may only apply if enrolling Cohorts B1 (2000 mg IV over 30 minutes) and Cohort C (up to 3000 mg IV over 90 minutes if 3000 mg is selected) simultaneously

m Clinic visits should be planned only when study samples need to be collected

Approved

VIR-7831  
Vir Biotechnology, Inc.

VIR-7831-5008 (GSK Study 217114)  
Amendment 4

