
VIR-7831  
Vir Biotechnology, Inc.

VIR-7831-5008 (GSK Study 217114)  
Amendment 4

Potential Risk of Clinical Significance	Summary of Data/Rationale for Risk	Mitigation Strategy
	
In the COMET-ICE study in participants with mild/moderate COVID-19 at high risk of progression, IRRs that occurred within 24 hours post infusion (pyrexia, chills, dizziness, dyspnea, pruritus, rash, and other infusion-related reaction) were reported in 6 (1%) of participants in the sotrovimab arm and 6 (1%) of participants in the placebo arm. All IRRs were nonserious, and Grade 1 or 2 severity and none led to treatment pausing or discontinuation. In the sotrovimab arm, all of the cases of IRRs were considered resolved and in the placebo arm, one participant had an event considered not resolved at the time of data cut-off. In COMET-ICE, all HSRs observed in the study were nonserious, of Grade 1 (mild) or Grade 2 (moderate) severity and reported in 2% of participants who received sotrovimab and in <1% who received placebo (9 participants treated with sotrovimab; 5 participants treated with placebo). None of the reactions in either arm led to pausing or discontinuation of the infusions. All events across both treatment groups were reported as resolved or resolving at the time of data cut-off.
 
No anaphylaxis events were reported in the COMET-ICE study in participants with mild to moderate COVID-19 not requiring hospitalization at study entry.
 
No anaphylaxis or serious hypersensitivity reactions were reported in the COMET-TAIL study in participants with mild to moderate COVID-19 not requiring hospitalization at study entry.
	
 
Investigational product will be administered in the clinic with staff trained in emergency care and resuscitation procedures with emergency care kit on hand during the study intervention administration and post-therapy observation periods.
 
Investigators will be instructed to discontinue IV infusions for participants who develop Grade 3 or higher infusion reactions.
 
If a participant experiences a Grade 2 IRR, investigators will be instructed to pause the infusion. The infusion may subsequently resume at a slower pace, at the investigator's discretion, and/or after symptomatic treatment (eg, antihistamines, IV fluids).
 
Infusion-related reactions including HSRs will be categorized as AESIs (as has been done in the past for other studies).
 

VIR-7831  

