Enhanced risk of systemic reactions including hypersensitivity reactions (SR/HSR) due to higher dose levels	
See "Infusion reactions including hypersensitivity reactions (HSR)"
 
It is possible that the risk of infusion reactions may be enhanced due to increase doses used, however as noted in the dose justification: the no-observed-adverse-effect-level for VIR-7831 was established when VIR-7831 was administered via IV infusion at 500 mg/kg (the highest dose tested) once a week for 2 weeks in cynomolgus monkeys (TX-7831-0102). Based on a preliminary population PK model for sotrovimab, the predicted <math>AUC_{inf}</math> following a 2000 mg IV dose is 21,400 <math>\mu\text{g}^*\text{day}/\text{mL}</math> and predicted <math>C_{max}</math> is 636 <math>\mu\text{g}/\text{mL}</math>. Based on the proposed 2000 mg IV dose, the margins based on nonclinical <math>C_{max}</math> and <math>AUC</math> margins of 21- and 10x, respectively, support the proposed clinical dose of 2 g IV. The <math>AUC_{inf}</math> following a 3 g IV dose is 32,100 <math>\mu\text{g}^*\text{day}/\text{mL}</math> and predicted <math>C_{max}</math> is 954 <math>\mu\text{g}/\text{mL}</math>. Based on the proposed 3000 mg IV dose, the margins based on nonclinical <math>C_{max}</math> and <math>AUC</math> margins of 14- and 7x, supporting the proposed doses up to 3000 mg.
	See Mitigation Strategy for "Infusion reactions including hypersensitivity reactions (HSR)"
Enhanced risk of systemic reactions including hypersensitivity reactions (SR/HSR) due to decreased infusion times	
See "Infusion reactions including hypersensitivity reactions (HSR)"
 
It is possible that decreased infusion times in Cohort B1 (30-minute infusion time of 2000 mg) and B2 (15-minute infusion time of 2000 mg) may enhance the possibility of a systemic reaction including hypersensitivity reactions (SR/HSR)
	See Mitigation Strategy for "Infusion reactions including hypersensitivity reactions (HSR)"

VIR-7831  
Vir Biotechnology, Inc.

VIR-7831-5008 (GSK Study 217114)  
Amendment 4

Potential Risk of Clinical Significance	Summary of Data/Rationale for Risk	Mitigation Strategy

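### Could an infusion reaction move a participant out of the cohort's row, because the Safety set is grouped by the infusion time actually received?

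*Protocol*

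**What the plan says.** Protocol Section 9.3 defines the Safety set as everyone enrolled and exposed, and adds: "Participants will be summarized according to actual dose and infusion time received during the study". The ITT set is defined as "All participants who were randomized and exposed to study intervention. Participants will be summarized according to the dose they were assigned to". It depends on randomization, and footnote l of the Schedule of Activities (Section 1.3) notes that "randomization may only apply if enrolling Cohorts B1 (2000 mg IV over 30 minutes) and Cohort C" at the same time.

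Section 8.4.9 lists infusion-related and hypersensitivity reactions among the adverse events of special interest (AESIs). Section 3 makes AESIs through Day 8 part of the primary endpoint.

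Section 2.3.1 describes what a reaction does to the infusion. For a Grade 2 reaction, "investigators will be instructed to pause the infusion. The infusion may subsequently resume at a slower pace". For more severe ones, "Investigators will be instructed to discontinue IV infusions for participants who develop Grade 3 or higher infusion reactions". Sections 7.1 and 7.1.1 also provide for stopping and pausing.

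Section 9.4 calls itself a summary and leaves detail to a substudy SAP, due before Cohort A is formally reported. That SAP was not supplied. The supplied SAP is version 2.0, based on Amendment 3, and covers the original intramuscular/intravenous part.

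**The concern.** Cohorts A, B1 and B2 all receive 2000 mg and differ only in infusion time (60, 30 and 15 minutes). A participant in B2 who reacts, is paused and resumes more slowly has an actual infusion time longer than 15 minutes. One whose infusion is stopped has received less than 2000 mg. If the Section 9.3 wording is applied to the minutes and milligrams delivered, that participant no longer fits the B2 row, and the event leaves with the participant. Membership of the row would then depend on the primary outcome, and the reaction rate for the fastest infusion would be biased downwards.

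Section 9.1 states the primary objective in terms of different infusion times, so reaction rates by regimen are a main result. The ITT set is no obvious substitute: it may be empty if B1 and C never enrol together, and it groups by dose alone. Start and stop times are recorded (Section 6.4), so the literal rule could be programmed.

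**Working it through.** **1. The plan's own figures.** The chance of seeing at least one event is 1 − (1 − p)^n.
- n = 200, p = 1.14%: 1 − 0.9886^200 = 89.9%.
- n = 50, p = 4.5%: 1 − 0.955^50 = 90.0%.

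Both agree with the 90% in Section 9.2. Exact (Clopper-Pearson) 95% intervals also reproduce Table 2: 3/50 gives 1.25% to 16.55%, and 10/200 gives 2.42% to 9.00%. No stated number is wrong.

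**2. What the literal reading could do.** Each reactor who leaves a row lowers its numerator and denominator by one. How many leave is an assumption.

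| Start (Table 2 row) | None leave | One leaves | Two leave |
|---|---|---|---|
| 3 of 50 | 6.0% (1.25–16.55) | 2/49 = 4.1% (0.50–13.98) | 1/48 = 2.1% (0.05–11.07) |
| 10 of 200 | 5.0% (2.42–9.00) | 9/199 = 4.5% (2.09–8.41) | 8/198 = 4.0% (1.76–7.81) |

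For detection, replace p by p(1 − f), where f is the assumed share of reactors regrouped. With n = 50 and p = 4.5%, the chance of at least one event in the row is 90.0%, 82.0%, 68.0%, 43.2% and 0% for f = 0, 25%, 50%, 75% and 100%.

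**3. How likely those starting rows are.** They come from a precision table and are not forecasts. Section 9.2 cites an infusion-reaction rate of 1.14% in COMET-ICE.
- Expected reactions: 50 × 0.0114 = 0.57, and 200 × 0.0114 = 2.28.
- Binomial chance of 3 or more in 50: 2.0%. Of 10 or more in 200: about 0.01%.
- At an assumed 2% (the hypersensitivity percentage for sotrovimab in Section 2.3.1), these become 7.8% and 0.7%.

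Rates at 2000 mg could be higher; the documents give none. Only a reaction that starts during the infusion can alter it, whereas the AESI definition runs to 24 hours after infusion and, for hypersensitivity, to any time after dosing.

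**4. Which reading the documents support.**
- Infusion time is a regimen label. Sections 1.1 and 4.1 list the infusion times as planned or optional, and Section 9.2 defines each cohort by one. Section 2.3.1 speaks of "decreased infusion times in Cohort B1 (30-minute infusion time of 2000 mg) and B2 (15-minute infusion time of 2000 mg"), which are planned durations.
- Section 9.2 and Table 2 give precision for single cohorts, for all 2000 mg cohorts combined and for the whole substudy. No category exists for altered infusions.
- Delivered minutes are a continuous quantity. Without cut-points they define no rows, and the protocol gives none.
- SAP Section 3 uses the same kind of phrase for its Safety set and then lists three fixed regimens as the possible values. SAP Section 4.5.1 counts interrupted and incomplete infusions separately. Section 4.5.2 tabulates events leading to interruption or discontinuation, and Section 6.1.1 summarises the duration of administration.

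Read this way, the word actual deals with a participant given another cohort's regimen in error. A participant whose infusion was interrupted stays in the row of the regimen started.

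**The case for a change.** The strongest case for a change is timing. The substudy is open label, and the safety review team includes sponsor statisticians who see accumulating data (Section 10.1.5). The substudy SAP need only be final before Cohort A is formally reported, so the grouping could be settled after reactions are known. One sentence written now would remove the doubt at almost no cost.

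Experience at 500 mg also reassures only in part. Section 2.3.1 reports of infusion reactions in COMET-ICE that "All IRRs were nonserious, and Grade 1 or 2 severity and none led to treatment pausing or discontinuation", and of hypersensitivity reactions that "None of the reactions in either arm led to pausing or discontinuation of the infusions". In the sotrovimab arm that is 0 of 6 and 0 of 9, with exact 95% upper limits of 46% and 34%. The text is silent on slowing, so these limits do not cover every alteration. Section 2.3.1 also accepts that higher doses and shorter infusions may raise the risk.

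What stands is that the wording is open, the supplied SAP does not govern the substudy, and the intended reading is inferred. What does not stand is that a biased result is likely. To regroup by delivered minutes, an analyst would have to invent categories the protocol lacks and depart from the convention already used in the same trial. The result would also be visible, because a 50-person cohort would be reported with fewer than its enrolled number.

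**Conclusion.** This is missing detail of a kind analysts fill sensibly, and it does not call for a change to the plan. The ordinary as-treated reading keeps a paused, slowed or stopped infusion in the row of the regimen started. The substudy SAP is the usual place to spell that out.

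Even on the literal reading, the damage is limited to descriptive rates by regimen. Listings of all adverse events (Section 9.4.1), the all-cohort totals and the cohort-by-cohort safety review (Section 9.5) would be unaffected, and there is no hypothesis test to distort. A slowed but completed 2000 mg infusion would also remain in the combined 2000 mg summary. If only Cohort A opens, there is no comparison between infusion times. If no infusion is altered, the effect is zero.

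The conclusion assumes that the substudy SAP follows the convention of the supplied SAP, which cannot be checked here. The illustrated shifts rest on assumed numbers of reactors moved.

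As a separate matter, Sections 2.3.1, 7.1 and 7.1.1 give different severity thresholds for pausing and stopping an infusion, and those passages must be reconciled. Nothing here depends on which applies.

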### 9.4. Statistical Analyses

The statistical analysis plan will be finalized prior to formal reporting of Cohort A for the sub-study and it will include a more detailed description of the statistical analyses described in this section. This section is a summary of the planned statistical analyses of the safety endpoints. All statistical analyses will be descriptive. The details of the descriptive summary statistics will be outlined in the statistical analysis plan.

Any change to the data analysis methods described in the protocol will require an amendment only if it changes a principal feature of the protocol. Any other change to the data analysis methods described in the protocol and the justification for making the change will be described in the statistical analysis plan. Additional exploratory analyses of the data will be conducted as deemed appropriate.

#### 9.4.1. Primary Endpoints

The primary objective of the safety substudy is to describe the safety and tolerability through Day 8 of high dose ascending intravenous sotrovimab. Summaries of AEs, SAEs, AESI, COVID-related AEs through Day 8 will be presented by MedDRA SOC and PT using frequency counts and percentages (i.e., number and percentage of subjects with an event). When summarizing the number and percentage of subjects with an event, subjects with multiple occurrences of the same AE will be counted once.

In addition, a listing containing individual subject level AE data for all deaths and other serious and significant AEs will be provided separately. All AEs, including pre- and post-treatment AEs, will be presented in individual subject data listings.

VIR-7831  
Vir Biotechnology, Inc.

VIR-7831-5008 (GSK Study 217114)  
Amendment 4

#### **9.4.2. Secondary Endpoint(s)**

Details of the analyses for the secondary endpoints will be provided in the statistical analysis plan.

#### **9.4.3. Exploratory Endpoint(s)**

Details of the analyses for the exploratory endpoints will be provided in the statistical analysis plan.

#### **9.4.4. Other Safety Analysis**

Number and percentage of subjects with AEs, SAEs, COVID-19 related AEs and COVID-19 related SAEs, and AESIs beyond Day 8, including laboratory tests and vital signs will be displayed in the form of listings, frequencies, summary statistics, and graphs where appropriate. Interpretation will be aided by clinical expertise.

To inform on the number and nature of non-COVID-19 adverse events and serious adverse events, additional safety analyses will be performed in which select, pre-specified terms consistent with known progression of COVID-19 disease will be excluded. Details of these and all analyses, including example outputs, will be documented in the statistical analysis plan.

#### **9.4.5. Other Analysis**

Full details of all analysis methods of immunogenicity and population pharmacokinetics will be provided in the statistical analysis plan.

### **9.5. Interim Analysis**

No interim analyses are planned. Note that the JSRT will review the safety and tolerability data from each cohort when all subjects in a cohort have completed Day 8. The details of the safety data review through Day 8 will be outlined in the statistical analysis plan.

### **9.6. Multiple Comparisons and Multiplicity**

No statistical testing will be conducted in the safety substudy.

## 10. SUPPORTING DOCUMENTATION AND OPERATIONAL CONSIDERATIONS

### 10.1. Appendix 1: Regulatory, Ethical, and Study Oversight Considerations

#### 10.1.1. Regulatory and Ethical Considerations

- This study will be conducted in accordance with the protocol and with:
  - Consensus ethical principles derived from international guidelines including the Declaration of Helsinki and Council for International Organizations of Medical Sciences (CIOMS) International Ethical Guidelines
  - Applicable ICH Good Clinical Practice (GCP) Guidelines
  - Applicable laws and regulations
- The protocol, protocol amendments, ICF, IB, and other relevant documents (e.g., advertisements) must be submitted to an IRB/IEC by the investigator and reviewed and approved by the IRB/IEC before the study is initiated.
- Any amendments to the protocol will require IEC/IRB approval before implementation of changes made to the study design, except for changes necessary to eliminate an immediate hazard to study participants.
- Protocols and any substantial amendments to the protocol will require health authority approval prior to initiation except for changes necessary to eliminate an immediate hazard to study participants.
- The investigator will be responsible for the following:
  - Providing written summaries of the status of the study to the IRB/IEC annually or more frequently in accordance with the requirements, policies, and procedures established by the IRB/EC
  - Notifying the IRB/IEC of SAE or other significant safety findings as required by IRB/IEC procedures
  - Providing oversight of the conduct of the study at the site and adherence to requirements of 21 CFR, ICH guidelines, the IRB/IEC, EU Clinical Trials Directive 2001/20/EC or Regulation (EU) No. 536/2014 (if applicable), and all other applicable local regulations

